### ECOG performance status

[figure not shown]
ECOG Performance Scale is provided in [Table 2-2](#) and is used to assess physical health of patients, ranging from 0 (most active) to 5 (dead):

**Table 2-2**      **ECOG performance scale**

Score	Description
0	Fully active, able to carry on all pre-disease performance without restriction

[figure not shown]
- 
- |   |   |
|---|---|
| 1 | Restricted in physically strenuous activity but ambulatory and able to carry out work of a light or sedentary nature, e.g., light house work, office work |
| 2 | Ambulatory and capable of all self-care but unable to carry out any work activities. Up and about more than 50% of waking hours                           |
| 3 | Capable of only limited self-care, confined to bed or chair more than 50% of waking hours   |
| 4 | Completely disabled. Cannot carry on any self-care. Totally confined to bed or chair  |
| 5 | Dead  |
- 

Shift tables of ECOG performance status at baseline to worst post-baseline ECOG status by score. ECOG performance status at each time point will be listed.

### 2.8.5 Pharmacogenetics/pharmacogenomics

Not applicable.

### 2.9 Sample size calculation

Based on [Simon's \(1989\)](#) optimal two-stage design, approximately 105 total patients are required to test a null hypothesis of ORR of 35% vs. an alternative hypothesis of ORR of 50% or more with a one-sided  $\alpha=0.05$  and 90% power. If at least 17 confirmed responses are

observed among 43 patients enrolled into Stage 1, an additional 62 patients will be enrolled into Stage 2. If 45 or more confirmed responses are observed among 105 total patients, the trial will be declared positive.

The operating characteristics of the design are described in [Table 2-3](#).

**Table 2-3 Operating characteristics of Simon's optimal two-stage design**

	True ORR			
	35% (null hypothesis)	40%	45%	50% (alternative hypothesis)
Probability stop for futility at Stage 1 (16 or fewer responses out of 43 patients enrolled at Stage 1)	0.683	0.418	0.192	0.063
Probability trial is success (45 or more responses out of 105 total patients)	0.049	0.268	0.642	0.900

## 2.10 Power for analysis of key secondary variables

Not applicable.

## 2.11 Interim analysis

In order to inform the recommendation to proceed to Stage 2 of the study, a data monitoring committee (DMC) will periodically review response data during Stage I, based on local investigator assessment, as defined in the DMC charter. The DMC may request data of assessment of response by the BIRC if deemed necessary to provide its recommendation. As per Simon's optimal two-stage design, the trial will be stopped at Stage 1 for futility if 16 or fewer responses are observed in the 43 patients enrolled to Stage 1. According to this rule, the DMC will make the recommendation to transition into the Stage 2 of the study. If at the time that the last patient is enrolled to Stage 1 a minimum of 17 responses have not yet been observed, accrual may be temporarily suspended until either the minimum number of 17 responses are observed or all 43 patients have been followed for at least 6 cycles of LDK378 or discontinued treatment.

Safety will be reviewed by the DMC regularly during the conduct of the study.

## 3 Changes to protocol specified analyses

This section contains to protocol-specified analyses and associated rationale for inclusion in Appendix 16.1.9 (Documentation of statistical methods) of the CSR.

**Table 3-1 Changes to protocol specified analysis or descriptions and rationale**

Protocol Section	Protocol Description	Change	Rationale
Section 10.1.2-Safety Set	The Safety Set will include all patients who receive at least one dose of LDK378	Changed to "The Safety Set consists of all patients who received at least one	This change from the protocol wording for and has been introduced in Section 2.2 of the RAP for

Protocol Section	Protocol Description	Change	Rationale
	and have at least one valid post-baseline safety assessment. The statement that a patient has no AE (on the Adverse Event eCRF) constitutes a valid safety assessment.	dose of study drug"	program clarification/simplification. It does not constitute a de facto change given that the DAR eCRF where the information on dosing is collected will also collect the reason for why the drug was discontinued which in itself constitutes a safety assessment
Section 10.1.3 - Per Protocol Set	The PPS will include patients who have an adequate tumor assessment at baseline, a follow-up tumor assessment >8 weeks after starting treatment (unless disease progression is observed before that time), and no major protocol deviation"s	Changed to "The PPS will include patients who have an adequate tumor assessment at baseline a follow-up tumor assessment >7 weeks after starting treatment (unless disease progression is observed before that time), and no major protocol deviations"	This change was made to take into consideration the +/-1 week window associated with tumor assessments
Section 10.5.3.3 - Laboratory abnormalities	Frequency tables for newly occurring on-treatment grades 3 or 4 will be provided separately for hematology and biochemistry laboratory tests	Deleted	One of the proposed analysis described in Section 2.8.2 of the RAP under Laboratory Abnormalities, is a shift table using CTC grades to compare baseline to the worst post-baseline value on treatment. The information that would be contained in the tabulation described in the protocol is similar to that contained within this shift table
Section 10.4 -	Reference is made to	The analysis for the	This change is made given

Protocol Section	Protocol Description	Change	Rationale
Primary Objective; Section 10.5.1 - Key Secondary Objective(s)	the calculation of 90% CIs given that the primary endpoint is tested at one-sided 5% significance level	primary endpoint will show the 90% CI as per protocol as well as 95% naive CIs. For other secondary endpoints only 95% CIs will be displayed	that across the LDK378 program, all efficacy endpoints are summarized using 95% CIs

## 4 Additional details on implementation of statistical methodology

The sections below contain additional details on statistical methodology that will be included in Appendix 16.1.9 (Documentation of statistical methods) of the CSR as well as rules details on programming rules that will be followed to implement the analyses described in Section 2.

### 4.1 Data included in the analyses

This section provides additional details to those included in [Section 2.1](#).

Final analysis of study data at the end of the study will include the data with an assessment date or event start date (e.g. vital sign assessment date or start date of an adverse event) prior to or on the cut-off date. For example, if the cut-off date is 30DEC2008, an AE starting on 28DEC2008 will be reported, whereas an adverse event starting on 31DEC2008 will not be reported.

### 4.2 Patient Classification into Analysis Sets

This section provides additional details to those included in [Section 2.2](#).

Patients are excluded from the analysis populations based on the protocol deviations entered in the database and/or on specific patient classification rules as shown in [Table 4-1](#) below. No analyses based on Per Protocol Set are planned in this final CSR.

**Table 4-1 Patient classification rules**

Analysis Population	Protocol deviation severity codes leading to exclusion	Additional patient classification rules leading to exclusion
Full Analysis Set	1, 3, 511	Not applicable
Safety Set	2, 3, 511	Not applicable
Per Protocol Set	4,511	Protocol deviations that will lead to removal of patients from Per Protocol Set (defined in Section 2.2 )

Severity code: 0= Include in everything, 1= Exclude from FAS, 2= Exclude from safety, 3= Exclude from FAS and safety, 4= Exclude from per-protocol, 511=exclude from all analysis

### 4.3 Last contact date

The last contact date is used for censoring in OS analyses and will be derived for patients not known to have died at the analysis cut-off using the latest complete date among the following:

- All patient assessment dates (e.g. blood draws, vital signs, performance status, patient reported outcomes, ECG, tumor assessments, etc)
- Concomitant medication start and end dates
- Start and end dates of antineoplastic therapies administered after study drug discontinuation.
- AE start and end dates
- Last known date patient alive collected on the 'Survival information' eCRF
- Study drug start and end dates
- Date of discontinuation on the 'End of treatment phase completion' and/or the 'Study phase completion' eCRFs.

If the last contact date as derived above is after the cut-off date then the cut-off date will be used. Only dates associated with patient visits or actual examinations of the patient will be used in the derivation. Dates associated with a technical operation unrelated to patient status such as the date a blood sample was processed will not be used.

### 4.4 Month derivation

For all derivations, a month will be calculated as  $(365.25 / 12) = 30.4375$  days. If duration is to be reported in months, duration in days will be divided by 30.4375.

### 4.5 Dose interruptions and dose changes

This section provides additional details to those included in [Section 2.6](#).

All calculations of dose interruptions and dose changes are based on the dose actually taken by the patient.

An interruption is defined as a 0 mg dose taken on one or more days. What follows defines how dose interruptions will be counted in the case of multiple dose interruptions.

- If an interruption occurs consecutively for at least two days due to the same reason, then it will be counted only once (example: *If the actual dose on days 1-3 is 750 mg and actual dose on days 4-5 is 0 mg and dose interruption on days 4-5 is due to AE, then the total number of dose interruptions is 1*).

- If an interruption occurs consecutively for at least two days due to different reasons, then it will be counted for each reason (*example: If the actual dose on days 1-3 is 750 mg and actual dose on days 4-5 is 0 mg and dose interruption on day 4 is due to AE and dose interruption on day 5 is due to dosing error, then the total number of dose interruptions is 2*).
- If an interruption occurs for more than one day due to the same reason, but the days are not consecutive, i.e. there is at least one dosing day in between, then each dose interruption will be counted as a different occurrence (*example: if the actual dose on days 1, 3 and 5, is 750 mg and actual dose on days 2 and 4 is 0mg, and dose interruptions on day 2 and 4 are both due to dosing error, the total number of dose interruptions is 2*).

A dose change is defined as a change to a lower or higher dose than the protocol planned dose e.g. 600 mg or 450 mg or 300 mg (reduction may be preceded by a 0 mg due to an interruption) in the daily administered dose, with an associated reason for dose change documented in the DAR summary eCRF page. *For example, in the sequence 750 mg - 0 mg - 600 mg, the 600 mg dose will be counted as a dose change, preceded by a 0 mg due to interruption (with reason documented) and 600 mg due to change (with reason documented).*

A dose interruption will not be counted as a dose change.

If a patient moves from a higher than protocol planned dose down to the planned dose then this will not be counted as a dose change, however if they move directly from a higher than planned dose down to a lower than protocol planned dose, then this will be counted as a dose change (with reason documented).

Dose reductions are a subset of dose changes where dose changes to higher than protocol planned dose are excluded.

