6.1.1 Dosing regimen

[figure not shown]
LDK378 will be administered orally once daily at a dose of 750 mg on a continuous dosing schedule. A complete cycle of treatment is defined as 28 days of once daily treatment of LDK378. The investigator must instruct the patient to take the study drug exactly as prescribed.

- Patients should take LDK378 on an empty stomach (i.e. fast from food and drink, except water) at least 1 hour before or 2 hours after a light meal.
- Each dose of LDK378 should be taken with a glass of water and consumed over as short a time as possible (i.e. not slower than 1 capsule every 2 minutes).
- Patients should be instructed to swallow whole capsules and not to chew or open them.
- If vomiting occurs during the course of treatment, no re-dosing of the patient is allowed before the next scheduled dose.
- Patients should be instructed not to make up missed doses or partial doses (i.e. when the entire dose is not taken as instructed). A missed or partial dose will be defined as a case when the full dose is not taken within 8 hours after the approximate time of the usually daily dosing. That day’s dose (or part remaining dose) should be omitted and the patient should continue treatment with the next scheduled dose on the following day.

Table 6-1 Dose and treatment schedule

Study treatments	Pharmaceutical form and route of administration	Dose	Frequency and/or Regimen
LDK378	Gelatin capsule for oral use	750 mg (5 x 150 mg capsule)	Once daily (28 day cycle)

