6.2.3 Criteria for LDK378 dose modifications

An LDK378 dose reduction will follow the guidelines described in [Table 6-2](#). For each patient, a maximum of 3 dose reductions will be allowed. All dose reductions will be in 150 mg decrements per reduction. The patient must be discontinued from treatment with LDK378 if further reduction is necessary.

Once the dose of LDK378 has been reduced due to toxicity, it cannot be re-escalated.

Table 6-2 Dose reduction steps for LDK378

LDK378 dose levels	Dose* and schedule
Starting dose level	750 mg qd continuously
Dose level – 1	600 mg qd continuously
Dose level – 2	450 mg qd continuously
Dose level – 3	300 mg qd continuously **

[figure not shown]
*Dose reduction should be based on the worst preceding toxicity as per NCI-CTCAE version 4.03
**Dose reduction below 300 mg/day is not allowed. If a dose reduction below 300 mg/day is required, the patient should be permanently discontinued from LDK378

Guidelines for dose modification and dose interruption of LDK378 are described in [Table 6-3](#).

[figure not shown]
Table 6-3 Criteria for interruption and re-initiation of LDK378 treatment

Dose changes must be recorded on the Dosage Administration Record eCRF.

[figure not shown]
Dose Modifications for LDK378 as specified in Section 6.2.3 .	
Worst toxicity (CTCAE 4.03 Grade)*	Dose Modifications for LDK378
HEMATOLOGICAL	
Neutropenia (ANC)	
Grade 1 (ANC < LLN - $1.5 \times 10^9/L$) Grade 2 (ANC < 1.5 and $\geq 1.0 \times 10^9/L$) Grade 3 (ANC < 1.0 and $\geq 0.5 \times 10^9/L$)	Maintain dose level
Grade 4 (ANC < $0.5 \times 10^9/L$)	Omit dose until resolved to \leq Grade 2, then: If resolved in ≤ 7 days, then maintain dose level If resolved in > 7 days, then $\downarrow 1$ dose level
Febrile neutropenia (ANC < $1.0 \times 10^9/L$, with a single temperature of ≥ 38.3 °C or a sustained temperature of ≥ 38 °C for more than one hour)	Omit dose until clinically resolved and neutropenia \leq Grade 2, then $\downarrow 1$ dose level
Thrombocytopenia	
Grade 1 (PLT < LLN - $75 \times 10^9/L$) Grade 2 (PLT < 75 and $\geq 50 \times 10^9/L$)	Maintain dose level
Grade 3 (PLT < 50 and $\geq 25 \times 10^9/L$)	Omit dose until resolved to \leq Grade 2, then: If resolved in ≤ 7 days, then maintain dose level If resolved in > 7 days, then $\downarrow 1$ dose level
Grade 4 (PLT < $25 \times 10^9/L$)	Omit dose until resolved to \leq Grade 2, then $\downarrow 1$ dose level
HEPATIC	
Alkaline phosphatase and/or GGT	

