10.5.3.5 Tolerability

Tolerability will be summarized in terms of dose reductions or drug interruption due to an AE.

[figure not shown]

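### SAP 4.5 classifies dose changes against the 750 mg planned dose instead of the patient's previous dose, so an increase between reduced levels is labelled a reduction and a return to 750 mg is not counted (minor)

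*SAP*

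**What the plan says.** The planned dose is fixed by Protocol 6.1.1: "LDK378 will be administered orally once daily at a dose of 750 mg on a continuous dosing schedule". SAP 2.6 uses the same 750 mg for relative dose intensity.

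SAP 4.5 builds its dose-change rules on that figure:

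- The data basis: "All calculations of dose interruptions and dose changes are based on the dose actually taken by the patient".
- A dose change: "A dose change is defined as a change to a lower or higher dose than the protocol planned dose". It must come "with an associated reason for dose change documented in the DAR summary eCRF page".
- A reduction: "Dose reductions are a subset of dose changes where dose changes to higher than protocol planned dose are excluded".
- A return to 750 mg from above: a patient who "moves from a higher than protocol planned dose down to the planned dose then this will not be counted as a dose change".

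The section says nothing explicit about a return to 750 mg from below, and it has no category for re-escalation. An interruption is not itself a dose change.

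SAP 2.6 then plans numbers and percentages of patients with changes, reductions or interruptions, together with the reasons, and a listing of all doses.

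On the protocol side, the text of section 6.2.3 describes reductions as steps of 150 mg downward, with at most three per patient, and adds: "Once the dose of LDK378 has been reduced due to toxicity, it cannot be re-escalated". Protocol 10.5.3.5 says: "Tolerability will be summarized in terms of dose reductions or drug interruption due to an AE".

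**The concern.** Neither the definition of a change nor that of a reduction refers to the dose the patient was on before. Two consequences follow from the wording. An upward move that stays below 750 mg meets the definition of a reduction, so its reason is tabulated among the reasons for reducing the dose. An upward move that ends at 750 mg is to a dose neither lower nor higher than planned, so it is not a dose change.

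Dose reductions are one of the two elements of the protocol's tolerability summary, and the protocol bars re-escalation after a reduction for toxicity. At stake are correct attribution of reasons, a reduction count that agrees with the protocol's three-step limit, and the ability to see re-escalations in the dose summaries. Efficacy endpoints, dose intensity and relative dose intensity do not use this rule.

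**Working it through.** **The two rules.** Both look at switches between successive non-zero doses and assume a reason is documented at each switch.

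- SAP 4.5, read literally: change if the new dose is not 750 mg; reduction if the new dose is below 750 mg.
- Previous-dose rule: change if the new dose differs from the last non-zero dose; reduction if lower, increase if higher.

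**The SAP's own example.** For 750 - 0 - 600 mg the SAP counts the 600 mg dose as one dose change and the 0 mg as an interruption. Both rules reproduce this. The example starts at 750 mg and only goes down, so it cannot show the problem.

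**Further paths.**

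| Dose path (mg) | SAP 4.5: changes / reductions | Previous dose: changes / reductions / increases |
|---|---|---|
| 750-0-600 | 1 / 1 | 1 / 1 / 0 |
| 750-600-450-300 | 3 / 3 | 3 / 3 / 0 |
| 750-600-450-600 | 3 / 3 | 3 / 2 / 1 |
| 750-600-750 | 1 / 1 | 2 / 1 / 1 |
| 750-600-450-600-750 | 3 / 3 | 4 / 2 / 2 |
| 750-600-450-300-450 | 4 / 4 | 4 / 3 / 1 |

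In the last row the SAP rule gives four reductions where the protocol allows three, although the patient stepped down only three times.

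**Where the rules differ.** All paths of one to five further steps from 750 mg were enumerated.

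- Doses 300, 450, 600 and 750 mg: 4 + 16 + 64 + 256 + 1024 = 1364 paths. The number of reductions differs in 771. Whether the patient was ever reduced, or ever had a change, differs in none.
- Of these, paths with no upward step: 4 + 10 + 20 + 35 + 56 = 125. The rules agree in all.
- Adding a dose above 750 mg (900 mg assumed): 5 + 25 + 125 + 625 + 3125 = 3905 paths. Ever reduced differs in 42.

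The zero in the first line is general. With doses up to 750 mg, a patient's first departure from 750 mg must be downward, and both rules call it a reduction.

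The 42 are also explained. The rules can disagree on ever reduced only when a patient never goes below 750 mg but steps from 900 back to 750 mg. Among paths of 750 and 900 mg, those of length L with such a step number 2^L - (L + 1), which for L = 1 to 5 is 0 + 1 + 4 + 11 + 26 = 42. That is the return the SAP deliberately leaves out.

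These path counts show where the rules diverge. They are not frequencies expected in patients.

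**The case against.** The strongest reply is that the planned output is at patient level. SAP 2.6 asks for patients with a reduction, that percentage does not move for doses up to 750 mg, and the SAP gives rules for totalling repeated interruptions but none for totalling reductions. This stands and limits the point to reasons, any per-patient count and visibility.

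Other safeguards also count. SAP 2.8.2 separately tabulates adverse events requiring dose adjustment or interruption, also for events of special interest, and does not say those tables use the 4.5 rule. SAP 2.4 tabulates treatment deviations, and SAP 2.6 lists every dose.

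Stronger readings that a reader might infer are not supported:

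- **A 50% overcount of reductions.** The path 750-600-450-600-750 gives 3 instead of 2, and (3 - 2)/2 = 50%, but this is one constructed path and a count that the SAP does not plan.
- **About 24 patients affected.** Applying the phase I rates in Protocol 1.2.1.2.1 to the 124 treated patients gives 0.584 x 124 = 72.4 with a reduction and (0.584 - 0.388) x 124 = 24.3 with more than one. The latter approximates the group in which a 450 to 600 mg move could arise, not the number in whom it did, which could be zero.
- **Forbidden re-escalations are hidden.** They have no row in the dose summaries, but they are in the listings and may be in the deviation tables; the full deviation list is in a data handling plan that is not part of these documents. The Amendment 2 log shows that the no-re-escalation guidance came when 45 patients (45/124 = 36%) had been treated. That makes earlier re-escalations possible, but they would not have breached guidance not yet issued.
- **A restart at the same reduced level, or a one-day partial intake, inflates reductions.** Each depends on a dose-change reason being recorded. For the restart, the SAP also requires a change in the dose given and says an interruption is not a dose change. Neither effect is established.
- **Protocol Table 6-2 defines a reduction relative to the current level.** The table lists levels below the starting dose; the decrement wording is in the text of section 6.2.3.

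The planned-dose reference is not just loose phrasing, however: the SAP's rules for moves from above 750 mg show that it was chosen deliberately.

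**Conclusion.** The definition does not match the protocol's meaning of a reduction and should be corrected, but the point is minor. Read literally, and provided a reason is documented, an increase between reduced levels is a reduction; a return from a reduced level to 750 mg is no change at all. The SAP states the second outcome outright only for a return from above; from below it follows from the definition.

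The percentage of patients with any reduction or any change is unaffected by the choice of reference dose, for patients who start at 750 mg and never exceed it. The results open to error are the reasons for reduction, any per-patient count, and the display of re-escalations in the dose summaries. How many patients are involved cannot be told from the documents. It is probably few, because the current protocol bars re-escalation after toxicity, leaving deviations, dosing errors, non-toxicity reasons and moves made before that guidance. The SAP is dated 12 April 2018 and the final cut-off is 22 January 2018, so the sponsor can count them directly from the dosing records.

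**What to change.** In SAP 4.5, compare each non-zero dose with the patient's last non-zero dose level, ignoring intervening 0 mg days:

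- lower: reduction;
- higher: re-escalation, including a return to 750 mg from below, tabulated separately with its reasons;
- same level after a hold: no dose change.

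Keep as an explicit exception, if still wanted, the existing rule that a return to 750 mg from above is not counted.

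Handle partial intakes recorded as dosing errors separately. State how they are identified, and do not count the return to full dose afterwards as a re-escalation; because the rule uses doses actually taken, false re-escalations would otherwise appear. This separation, unlike the change of reference dose, could lower the percentage ever reduced if a patient's only dose below 750 mg was such an intake with a dose-change reason recorded.

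The cost is the SAP wording, a line recording the change, and one derived variable from the Dosage Administration Record. No new data are needed and no treatment rule changes.
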